7.6 Immunogenicity Analysis

Immunogenicity will be reported for ADA positive status (such as persistent positive, neutralizing positive, only last sample positive, baseline positive, and other positive) and ADA negative status,

relative to baseline. [REDACTED]

Incidence of ADA

Number (%) of subjects will be reported for the following parameters based on Evaluable Subjects.

- Baseline ADA-positive
- ADA-positive
 - Persistent Positive (PP)
 - Not PP-Last Sample Positive
 - Other positive
 - Neutralizing Positive
- ADA-negative

A listing of all ADA assessments will be provided. A separate listing of ADA assessments for subjects with neutralizing positive will also be provided as appropriate.

Clinical implications

Clinical implications of nivolumab immunogenicity will be primarily focused on subjects with persistent ADA-positive relative to ADA-negative. Subjects with any ADA-positive samples after initiation of treatment (relative to baseline) may be used to explore clinical implications. Effect of immunogenicity on safety will be explored by examining the frequency and type of AEs of special interest such as hypersensitivity/infusion reaction. Summary tables for incidence of overall and each of the preferred terms will be provided, if the number of subjects is of sufficient size (e.g., at least 10 subjects). Otherwise, individual subject's safety profile will be examined and described based on a listing.

7.7 Pharmacokinetics

Summary statistics will be calculated for nivolumab and daratumumab concentrations, and summarized by scheduled sample collection time.

8 CONVENTIONS

The following conventions may be used for imputing partial dates for analyses requiring dates:

- For missing and partial adverse event onset dates, imputation will be performed using the Adverse Event Domain Requirements Specification⁴
- For missing and partial adverse event resolution dates, imputation will be performed as follows:
 - If only the day of the month is missing, the last day of the month will be used to replace the missing day. If the imputed date is after the death date or the last known alive date, then the latest known alive date or death date is considered as the resolution date.
 - If the day and month are missing or a date is completely missing, it will be considered as missing.

- Missing and partial non-study medication domain dates will be imputed using the derivation algorithm described in 4.1.3 of BMS Non-Study Medication Domain Requirements Specification⁵.

- For death dates, the following conventions will be used for imputing partial dates:
 - If only the day of the month is missing, the 1st of the month will be used to replace the missing day. The imputed date will be compared to the last known alive date and the maximum will be considered as the death date.
 - If the month or the year is missing, the death date will be imputed as the last known alive date.
 - If the date is completely missing but the reason for death is present, the death date will be imputed as the last known date alive.
- For date of progression after start of study therapy, the following conventions will be used for imputing partial dates:
 - If only the day of the month is missing, the 1st of the month will be used to replace the missing day. In case of the date of death is present and complete, the imputed progression date will be compared to the date of death. The minimum of the imputed progression date and date of death will be considered as the date of progression.
 - If the day and month are missing or a date is completely missing, it will be considered as missing.
- For date of progression to prior therapies, the following conventions will be used for imputing partial dates:
 - If only the day of the month is missing, the 1st of the month will be used to replace the missing day.
 - If the day and month are missing or a date is completely missing, it will be considered as missing.
- For other partial/missing dates, the following conventions were used:
 - If only the day of the month is missing, the 15th of the month will be used to replace the missing day.
 - If both the day and the month are missing, “July 1” will be used to replace the missing information.
 - If a date is completely missing, it will be considered as missing.

The following conversion factors will be used to convert days to months or years:

$$1 \text{ month} = 30.4375 \text{ days and } 1 \text{ year} = 365.25 \text{ days.}$$

Duration (e.g. time-to onset, time-to resolution) will be calculated as follows:

$$\text{Duration} = (\text{Last date} - \text{first date} + 1)$$

Last known alive date will be defined based on all appropriate dates collected on the CRF.

All statistical analyses will be carried out using SAS (Statistical Analysis System software, SAS Institute, North Carolina, USA) unless otherwise noted.

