4.1.3 Duration of Response

Duration of Response (DOR) is defined as the time between the date of first documented response (CR or PR) to the date of the first documented tumor progression as determined by Investigator (per RECIST v1.1 criteria), or death due to any cause, whichever occurs first. Subjects who start subsequent therapy without a prior reported progression will be censored at the last evaluable tumor assessments prior to initiation of the subsequent anticancer therapy. Subsequent therapy includes any therapy (systemic cancer therapy, surgery, radiotherapy). Subjects who die without a reported prior progression will be considered to have progressed on the date of their death. For subjects who neither progress nor die, DOR will be censored on the date of their last evaluable tumor assessment. DOR will be evaluated for responders (CR or PR) only.

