4.1.4 Progression-Free Survival

PFS rate at time T is defined as the probability that a subject has not progressed and is alive at time T following start of treatment. PFS rates at fixed time points (e.g. 6 months, depending on the minimum follow-up) are defined as the probability that a subject has not progressed and is alive at time T following start treatment date.

Disease assessment with CT and/or MRI, as appropriate, will be performed at baseline and every 6 weeks up to 24 weeks, and every 12 weeks thereafter until PD, the completion of follow-up, initiation of new therapy, or participant withdraw from the study. Tumor responses will be assessed by the investigator as defined by RECIST v1.1.

PFS is defined as the time between the date of treatment start day and the date of first documented tumor progression, based on Investigator assessments (per RECIST v1.1 criteria), or death due to any cause, whichever occurs first.

Subjects who die without a reported progression will be considered to have progressed on the date of their death. The following censoring rules will be applied for the primary definition of PFS:

- Subjects who did not progress or die will be censored on the date of their last evaluable tumor assessment.
- Subjects who did not have any on study tumor assessments and did not die will be censored on their first dosing date.
- Subjects who receive subsequent anti-cancer therapy prior to documented progression will be censored at the date of the last evaluable tumor assessment conducted on or prior to the date of initiation of the subsequent anti-cancer therapy.
- Subjects who did not have a documented progression and received subsequent anti-cancer therapy will be censored at the date of the last evaluable tumor assessment conducted on or prior to the initiation of the subsequent anti-cancer therapy.
- Subsequent therapy includes any therapy (systemic cancer therapy, surgery, radiotherapy).

Censoring rules for the primary definition of PFS are presented in Table 4.1.4-1.

Table 4.1.4-1: Censoring Scheme used in Primary Definition of PFS

Situation	Date of Progression or Censoring	Outcome
No baseline tumor assessments*	Date of first dose	Censored
No on study tumor assessments and no death*	Date of first dose	Censored

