Subsequent anti-cancer therapy started without death or progression per RECIST v1.1 reported prior or on the same day	Date of last evaluable tumor assessment prior to or on the date of initiation of the subsequent anti-cancer therapy	Censored
Documented progression per RECIST v1.1 and no new anti-cancer started before	Date of the first documented progression per RECIST v1.1 (excludes clinical progression)	Progressed
No progression and no death, and no new anti-cancer therapy started	Date of last evaluable tumor assessment	Censored
Death without progression per RECIST v1.1 and no new anti-cancer started before	Date of death	Progressed

* Tumor assessments and death if any, occurring after start of subsequent anti-cancer therapy are not considered.

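### SAP 8 discards a recorded year of death when the month is missing, so a few PFS or DOR events could be dated before the year in which the death is recorded (minor)

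*SAP*

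**What the plan says.** SAP section 8 has three rules for death dates.

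- Only the day missing: the first of the recorded month is inserted, and then "The imputed date will be compared to the last known alive date and the maximum will be considered as the death date".
- Month or year missing: "If the month or the year is missing, the death date will be imputed as the last known alive date".
- Nothing recorded except a reason for death: "If the date is completely missing but the reason for death is present, the death date will be imputed as the last known date alive".

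Where a date has no specific rule, the same section keeps the year: "If both the day and the month are missing", 1 July is inserted. The last known alive date is defined broadly: "Last known alive date will be defined based on all appropriate dates collected on the CRF".

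The death date enters two secondary endpoints. For PFS (SAP 4.1.4): "Subjects who die without a reported progression will be considered to have progressed on the date of their death". For DOR (SAP 4.1.3): "Subjects who die without a reported prior progression will be considered to have progressed on the date of their death". Table 4.1.4-1 limits which deaths count for PFS: "Death without progression per RECIST v1.1 and no new anti-cancer started before".

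**The concern.** The word *or* in the second rule treats a date with a known year and unknown month as if nothing were known. No later step compares the result with the recorded year. A participant last known alive in 2018, with death recorded as 2019, is therefore given a death date in 2018. That is a date the data rule out, so this goes beyond a choice between reasonable imputations.

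It also departs from the neighbouring rules. The day-missing rule keeps the recorded month and year and uses the last known alive date only as a lower bound. The rule for other dates keeps the year. The SAP gives no reason for treating a death with a known year differently.

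At stake is the timing of some PFS and DOR events, which would be placed too early. No sensitivity analysis in the SAP would show this.

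**Working it through.** The plan attaches no figure to this rule, so there is none to reproduce. The check applies the rule to dates and compares the result with the recorded year. All dates below are assumed examples. Months use the SAP 8 factor of 30.4375 days.

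**Size of the error for one death.** Let L be the last known alive date, in 2018, with death recorded only as 2019. The rule imputes L. The true date lies between 1-Jan-2019 and 31-Dec-2019, so:

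- minimum error = 1-Jan-2019 − L
- maximum error = 31-Dec-2019 − L

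| L | Minimum error | Maximum error |
|---|---|---|
| 15-Mar-2018 | 292 days (9.6 months) | 656 days (21.6 months) |
| 30-Jun-2018 | 185 days (6.1 months) | 549 days (18.0 months) |
| 20-Sep-2018 | 103 days (3.4 months) | 467 days (15.3 months) |
| 30-Nov-2018 | 32 days (1.1 months) | 396 days (13.0 months) |
| 20-Dec-2018 | 12 days (0.4 months) | 376 days (12.4 months) |
| 31-Dec-2018 | 1 day | 365 days (12.0 months) |

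**Effect on one PFS time.** Assume first dose on 15-Jan-2018 and L = 30-Jun-2018. SAP 8 defines duration as last date − first date + 1.

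- SAP rule: (166 + 1) / 30.4375 = 5.49 months.
- Earliest date consistent with the record, 1-Jan-2019: (351 + 1) / 30.4375 = 11.56 months.

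**Typical error.** Assume L is spread evenly over a 365-day year and death follows L by an exponential lag. Simulation, keeping deaths that fall in the next calendar year, gives these median errors. The last column uses 1 January of the recorded year instead.

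| Mean lag | SAP rule | 1 January rule |
|---|---|---|
| 14 days | 0.8 months | 0.3 months |
| 28 days | 1.5 months | 0.6 months |
| 60 days | 3.3 months | 1.4 months |
| 90 days | 4.8 months | 2.0 months |

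**Limit set by scheduled contact.** After Week 24, scans are 12 weeks apart, ± 2 weeks (Protocol Table 9.1.1-2). The widest permitted gap is 84 + 14 + 14 = 112 days, or 112 / 30.4375 = 3.7 months. While scans are kept, the error cannot exceed about that. The 185-day and 292-day examples require missed contact.

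**Effect on the curve.** With 40 treated and no censoring, one misplaced death lowers the PFS curve by 1/40 = 2.5 percentage points between the imputed and the true date. In the NSCLC cohort, fewer than 20 had been treated when the combination was discontinued (SAP, Schedule of Analyses), so the step exceeds 1/20 = 5 points. Censoring makes the step larger.

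**Which deaths are affected.** All of these must hold:

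1. the year of death is recorded and the month is not;
2. L falls in an earlier calendar year;
3. there is no earlier RECIST progression;
4. no subsequent therapy was started before death;
5. for DOR, the participant is also a responder.

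If L falls in the recorded year of death, the present rule and the fix below give the same date.

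**The case against.** The strongest objection is that few deaths, perhaps none, will meet all these conditions. Participants whose deaths count for PFS are by design still in contact: treatment visits every 4 weeks from Week 25, follow-up visits at Days 30 and 100, and scans until progression or new therapy (Protocol Section 2 and Table 9.1.1-2). Deaths within 100 days of the last dose are SAEs reportable within 24 hours (Protocol 9.2.1 and Appendix 3), and sites must try to obtain the date of death (Protocol 8.3). In addition, this is a close-out synoptic report of a discontinued study, PFS and DOR are secondary, and no p-values are planned (SAP 7.4). All of this stands and limits the importance of the point. It does not make the rule correct.

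Three stronger readings are tempting, but the documents do not support them.

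- *A false safety signal.* A reader might infer that early death dates would show deaths close to the last dose that did not occur then. SAP 7.5.1 plans only a by-subject listing of deaths, and nothing says that it prints imputed dates. The AE and SAE tables use a 30-day window on onset dates, which have their own imputation specification (SAP 6.1, 7.5.2 to 7.5.4 and 8).
- *Always months too early.* The guaranteed error can be a single day.
- *A lower median.* If the imputed and true dates lie on the same side of the median, it need not move.

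The opening of SAP 8 says that the conventions *may* be used. That is little defence, because the death-date bullets themselves say *will* and offer no alternative.

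**Conclusion.** The rule is wrong as written whenever the year of death is recorded, the month is missing and the last known alive date falls in an earlier year. The imputed date is then impossible on the trial's own data, by at least one day and possibly by many months.

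The bias is towards shorter PFS and DOR. ORR, DCR, whether a PFS or DOR event occurred, and the AE and SAE tables are unaffected. The number of affected deaths is not given in the documents and is probably very small. The error sizes above rest on assumed dates and an assumed lag; the contradiction with the recorded year does not. This is a minor point, worth correcting because the correction is simple.

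**What to change.** In SAP section 8, replace the rule for a missing month or year of death with:

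*If the month is missing and the year is recorded, use the later of 1 January of that year and the last known alive date. If the year is missing, use the last known alive date.*

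This extends the later-of-two-dates approach that the SAP already uses when only the day is missing. The first day of the year is the counterpart of the first day of the month. It remains an early imputation and can still be up to about a year before the true date, but it no longer contradicts the record. Using 1 July, as for other dates, with the same lower bound would also respect the recorded year. The choice between them is a convention.

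The cost is one sentence in the SAP and one line of derivation code. No additional data are needed.

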4.1.1 Objective Response Rate

Objective Response Rate (ORR) is defined as the number of treated subjects who achieve a best response of complete response (CR) or partial response (PR) based on investigator assessments (using RECIST v1.1 criteria) divided by the number of all treated subjects. Best Overall Response (BOR) is defined as the best response, as determined by Investigator, recorded between the date of first dose and the date of objectively documented progression per RECIST v1.1 criteria or the date of subsequent therapy, whichever occurs first. For subjects without documented progression or subsequent therapy, all available response designations will contribute to the BOR determination. Subsequent therapy includes any therapy (systemic cancer therapy, surgery, radiotherapy).

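### SAP Section 8 gives an imputed progression date no lower bound, so in rare cases progression can be dated before first dose or before an earlier non-progression scan (wrong as written, minor)

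*SAP*

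**What the plan says.** SAP Section 8 opens its date rules permissively: "The following conventions may be used for imputing partial dates for analyses requiring dates". The rule at issue is introduced by "For date of progression after start of study therapy, the following conventions will be used for imputing partial dates". It reads "If only the day of the month is missing, the 1st of the month will be used to replace the missing day", and where a complete death date exists it adds "The minimum of the imputed progression date and date of death will be considered as the date of progression". It makes no comparison with first dose or with any earlier scan.

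The death-date rule just above it also imputes the 1st of the month, but protects the other side: "The imputed date will be compared to the last known alive date and the maximum will be considered as the death date".

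Two definitions use the progression date:

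- SAP 4.1.4: "PFS is defined as the time between the date of treatment start day and the date of first documented tumor progression", or death.
- SAP 4.1.1: best overall response (BOR) is the best response "recorded between the date of first dose and the date of objectively documented progression per RECIST v1.1 criteria", or up to subsequent therapy if that comes first.

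No other section of the SAP or protocol supplies a lower bound.

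**The concern.** Moving a date back to the 1st of its month can only make it too early, so the side that needs a guard is the lower one. The SAP guards the upper side. As written, the rule can therefore return a value that contradicts the recorded data: progression before treatment began, or before a scan that showed none.

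The first case gives a PFS of zero or less. The second pushes a recorded response, confirming or stable-disease scan outside the BOR window, and can change that participant's ORR or disease control status.

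Cohorts are about 40, and SAP Section 5 puts the line for excluding a 10% ORR between 8 responders (lower bound 9.1%) and 9. One participant can therefore show in the summary. Because the rule states how to compute the value, this is more than a missing detail.

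**Working it through.** The plan gives no figure to reproduce, so the check applies the rule to dates.

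**Inputs**
- Imputation, cap and BOR window: as quoted from SAP Sections 8 and 4.1.1.
- Duration = last date - first date + 1 (SAP Section 8).
- Scans every 6 weeks ±1 week to week 24, then every 12 weeks ±2 weeks (Protocol Table 9.1.1-2). The earliest scheduled scan is 42 - 7 = 35 days after first dose. The smallest gap between 6-weekly scans is 42 - 7 - 7 = 28 days.
- CR/PR confirmed after at least 4 weeks; stable disease needs at least 35 days (Protocol Section 9.1.1 and Appendix 7).
- Assumption: calendar dates spread evenly over 365 days (seven 31-day months, four 30-day months, one 28-day month).

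**1. Does the cap at death ever act?** The 1st of the progression month is never later than the true progression date, which is never later than death. For consistent dates the minimum never changes anything.

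**2. Progression before first dose.** Let first dose fall on day *d* of a month of length *m*, with progression *k* days later. The imputed date precedes first dose when *d* > 1 and *d* + *k* ≤ *m*. Then PFS = 1 - *d* + 1 = 2 - *d*: zero for *d* = 2 and -28 for *d* = 30. A first dose on the 1st gives PFS = 1. The largest possible *k* is 31 - 2 = 29.
- First scheduled scan (*k* = 35 to 49): 0%. The smallest imputed PFS is 6 days (first dose 24 February, progression 31 March, imputed 1 March: 5 + 1).
- Unscheduled scan, *k* uniform on 1 to 30: each *k* leaves *m* - *k* - 1 first-dose dates per month. Summed over *k*, this is 435 for a 31-day month, 406 for a 30-day month and 351 for February. (7×435 + 4×406 + 351) / (365×30) = 5,020 / 10,950 = 46%.

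**3. Progression before the preceding non-progression scan.** For a gap of *g* days the share is Σ max(*m* - *g* - 1, 0) / 365.
- *g* = 7: (365 - 12×8)/365 = 74%
- *g* = 14: (365 - 12×15)/365 = 51%
- *g* = 21: (365 - 12×22)/365 = 28%
- *g* = 28: (7×2 + 4×1)/365 = 18/365 = 5%
- Scheduled 6-weekly scans, all 365×15×15 = 82,125 combinations: a 28-day gap occurs in one window combination (18 dates) and a 29-day gap in two (7 dates each). (18 + 14)/82,125 = 0.04%.
- Scheduled 12-weekly scans: smallest gap 84 - 14 - 14 = 56 days, so 0%.

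**4. Worked dates (assumed; day of the progression scan missing)**

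| Case | First dose | Earlier scans | Progression scan | SAP date | PFS true / SAP / with floor |
|---|---|---|---|---|---|
| A | 10 Mar | none | 28 Mar, unscheduled | 1 Mar | 19 / -8 / 1 |
| B | 3 Oct | PR 14 Nov; confirming PR 2 Jan | 30 Jan | 1 Jan | 120 / 91 / 93 |
| C | 3 Oct | SD 14 Nov | 28 Nov, unscheduled | 1 Nov | 57 / 30 / 44 |

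In B every scan is inside its window (day 42; 84 + 7 = 91; 126 - 7 = 119). The confirming scan falls after the imputed progression. PR followed by progression then becomes stable disease under Appendix 7 Table 2 (day 42 meets the 35-day minimum), so a responder is lost from ORR. In C the stable-disease scan is displaced, and best response becomes progression.

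**5. General shift from using the 1st.** (7×465 + 4×435 + 378)/365 = 5,373/365 = 14.7 days on average, 30 at most. This does not depend on a floor. In B the date is 29 days early without the floor and 27 days early with it.

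**The case against.** The case for leaving the text alone is substantial.

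- **Rarity.** The PFS event is RECIST-documented progression and Table 4.1.4-1 excludes clinical progression, so it normally rests on a dated scan. Nothing in the documents shows that any progression date is partial. This stands, and it sets the size of the point.
- **Schedule.** Under protocol timing the failures almost disappear (0% and 0.04%). The 46% and the 5% to 74% figures are conditional on both an unscheduled scan and a missing day. This stands.
- **Lost responses.** Confirmation takes at least 4 weeks, so a first response and its confirming scan will almost never both share the progression month. Normally only the confirming scan can be displaced. This stands, but case B shows that it is enough.
- **Wording.** The conventions are permissive, and the rule is headed as applying to progression after the start of therapy. A pre-dose result would contradict that heading. But the heading labels the category and does not constrain the imputed value, and permissive wording leaves an impossible date to the programmer.
- **Consequence.** ORR, PFS and DOR are secondary, SAP 7.4 reports no p-values, and SAP version 2.0 serves a close-out synoptic report. No test or decision turns on this.

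A reader might infer that the missing floor biases PFS and DOR downward by about two weeks. The documents do not support that. The 14.7-day shift comes from choosing the 1st of the month and applies only to partial dates. For progression at the first scheduled scan, a floor at first dose never acts.

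**Conclusion.** The point holds as a minor error in a stated rule. SAP Section 8 can return a progression date that is impossible against the participant's own data. Its only bound works in the direction that cannot fail, and the parallel death rule shows the missing protection. The consequences are a PFS of zero or less when first dose falls on the 2nd or later of the progression month, and loss of a scan from the BOR window when an earlier non-progression scan falls in that month.

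Affected participants are probably very few, perhaps none. The percentages rest on evenly spread calendar dates, and the number of partial progression dates and unscheduled scans is unknown. Case B also assumes that the protocol's confirmation requirement is applied in deriving ORR. The documents do not support a claim of general bias in PFS, DOR or ORR.

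**What to change.** Add to the progression-date rule in SAP Section 8:

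> The imputed progression date will be the latest of the 1st of the month, the date of first dose, and the day after the last evaluable tumor assessment without progression that precedes the recorded first progression assessment; it will be no later than the date of death.

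The limit to assessments preceding the first recorded progression is needed. Protocol Section 7.1.5 allows treatment beyond initial progression with a repeat scan, and Section 9.1.1 asks for confirmation scans. Without that limit, a later non-progression scan could push the date past its true month. Because the day is missing, the order should come from the assessment sequence and not from the date.

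The cost is one SAP sentence and one line of derivation code, with no new data. The sentence does not address the 14.7-day average shift, which would need a different imputation day.

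### SAP Section 8 names no rule for partial start dates of subsequent radiotherapy or surgery; under its unbounded catch-all, therapy that followed a progression can be dated before it, turning a PFS event into a censoring

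*SAP*

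**What the plan says.** SAP Section 8 gives separate treatment to adverse event onset and resolution, non-study medication, death, on-study progression and progression on prior therapies. Medication dates go to an outside document: "Missing and partial non-study medication domain dates will be imputed using the derivation algorithm described in 4.1.3 of BMS Non-Study Medication Domain Requirements Specification". Everything else falls under a catch-all: "For other partial/missing dates, the following conventions were used". Its rules are "If only the day of the month is missing, the 15th of the month will be used to replace the missing day" and "If both the day and the month are missing, “July 1” will be used to replace the missing information". Neither compares the result with another date. The death rule in the same section does: "The imputed date will be compared to the last known alive date and the maximum will be considered as the death date".

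SAP Section 4.1.4 counts surgery and radiotherapy, as well as systemic treatment, as subsequent therapy. Table 4.1.4-1 then uses the therapy start date to decide the outcome:

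- A participant is censored at the last evaluable scan on or before that start in the situation "Subsequent anti-cancer therapy started without death or progression per RECIST v1.1 reported prior or on the same day".
- A progression is an event only in the situation "Documented progression per RECIST v1.1 and no new anti-cancer started before".

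The same start date closes the window for best overall response (SAP 4.1.1) and censors duration of response (SAP 4.1.3).

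**The concern.** No rule in Section 8 names radiotherapy or surgery, and neither is a medication in the ordinary sense. On the SAP's own text, a partial start date for either goes to the catch-all. That default can contradict the known order of events. When therapy was given after a documented progression and its day was not recorded, the 15th may fall before the progression, and the censoring rule then discards a real event.

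Two records show this (dates illustrative):

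- **Day missing.** Progression on 20 September 2018, previous scan on 9 August (6 weeks earlier), radiotherapy on 27 September recorded only as September 2018. The imputed start is 15 September. The participant moves from an event on 20 September to a censoring on 9 August.
- **Day and month missing.** Same progression, therapy recorded only as 2018. The imputed start is 1 July. The progression no longer counts, and censoring moves back to the last evaluable scan on or before 1 July.

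At stake are the Kaplan-Meier estimates of PFS and duration of response, and any response recorded between the imputed and the true start date.

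**Working it through.** The plan gives no figure on this point, so there is none to reproduce. The check applies the Section 8 rule to Table 4.1.4-1.

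**When a reversal occurs.** Progression on the same day as therapy still counts as an event, so the imputed date must be strictly earlier than the progression.

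- Day missing: progression on day 16 or later, with therapy later in the same month. Therapy in a later month goes to the 15th of that month and stays after the progression.
- Day and month missing: progression on 2 July or later, with therapy later in the same year.
- No reversal if therapy lacks only the day and the progression day is also missing in that month: the progression goes to the 1st.

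**Share of day-missing records reversed.** Assumptions: a 30-day month, progression day d uniform on 1 to 30, therapy lag uniform on 1 to L days after progression. For each d from 16 to 30, the reversing lags number min(L, 30 − d). Dividing the sum by 30 × L gives:

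| L (days) | Reversing pairs | All pairs | Share |
|---|---|---|---|
| 7 | 77 | 210 | 37% |
| 14 | 105 | 420 | 25% |
| 28 | 105 | 840 | 12.5% |

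The lag assumption drives the result. Enumerating every progression date in 2018 gives 39% for lags of 0–7 days, 28% for 0–14, 13% for 0–30, 6% for 7–28 and 0.2% for 14–42.

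**Day and month missing.** The same enumeration gives 42% to 49% across those lag ranges.

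**The reverse error.** Radiotherapy on 10 September with progression on 14 September should be censored. With the day missing, therapy is dated 15 September and the progression counts. For therapy 1–30 days before progression, the pairs are d = 1 to 15 with lag at most d − 1: 105 of 30 × 30 = 900, or 11.7% (11.5% by enumeration over 2018). With the month also missing it is 46%. For therapy 1–30 days after progression, the day-missing share is also 105/900 = 11.7%. Under these assumptions the two errors are equally likely per record, so the net direction depends on how often therapy follows rather than precedes progression.

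**Effect of one reversal.** One event is lost, and the time moves back to the previous evaluable scan: about 6 weeks up to Week 24, about 12 weeks later (SAP 4.1.4), or further under July 1. For scale only, in simulated cohorts of 40 with exponential PFS, assumed medians of 2 and 4 months and no other censoring, turning 1, 2 or 4 events into censorings raised 26-week PFS by about 0.7–1.0, 1.4–1.7 or 2.7–3.6 percentage points. These counts are inputs, not estimates.

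**After the fix.** With the imputed date held no earlier than a documented progression in the same known month (or the same known year), all 2018 progression dates with lags of 0–30 days gave 0 reversals.

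**The case against.** The strongest objection is that the governing rule may lie outside the SAP. If the sponsor's non-study medication domain includes radiotherapy and surgery, its own algorithm applies and the catch-all is never reached. The documents neither confirm nor exclude this. The SAP lists those two apart from systemic therapy, which favours the catch-all reading without proving it. This stands as a condition on the point. It does not remove the need for the SAP to say which rule applies.

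The consequence is also small. Systemic therapy is under the external rule in any case. Protocol Appendix 2 limits blank case report form fields to permitted circumstances, so partial dates may be few. PFS and duration of response are secondary, no p-values are reported (SAP 7.4), and the report is a synoptic close-out. Section 8 is worded permissively, so the programmer may not be bound by it. All of this limits the importance of the point. None of it makes the default correct where it applies.

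A reader might go further and infer that the rule biases PFS upward. The documents do not support that as a general statement, because the reverse error exists and nothing in them says how often therapy follows progression. Upward bias can be claimed only for records where therapy came after progression.

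**Conclusion.** The point holds as a minor gap in specification with a definite consequence. If the catch-all governs radiotherapy and surgery dates, the rule as written can turn a real PFS event into a censoring, and can also do the opposite. The same date affects best overall response and duration of response.

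The size per affected record depends on the assumed lag: about 37%, 25% and 12.5% of day-missing records for therapy within 7, 14 and 28 days of progression, with progression day uniform. A reader might restrict to therapy in the same month as progression, which gives 77/182 = 42%, 105/315 = 33% and 105/434 = 24%, and multiply by a guessed number of partial dates. That does not work: those shares apply only to same-month therapy, and the documents give no number of partial dates. No count of lost events can be stated.

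**What to change.** State in SAP Section 8 which rule governs start dates of subsequent radiotherapy and surgery. If it is the external specification, one line is enough. If it is the catch-all, add before database lock:

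- When a documented progression falls in the same known month (or the same known year, if the month is missing), the imputed therapy date is no earlier than the progression date.
- The imputed date stays within the known month or year, no earlier than first dose and no later than death or last known alive date.
- Affected participants are listed, and PFS is shown under both assignments.

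A floor at the last study dose should not be used. Protocol Section 8.1.2 anticipates palliative radiotherapy during a dosing delay, so such a floor could move on-treatment radiotherapy out of its recorded month.

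The cost is a few sentences and a small programming change. The downside is that therapy truly started shortly before progression in the same period would count as an event. The wider the missing period, the more such cases it takes in, which is why both assignments should be shown. For participants who stopped treatment before progression, Protocol Table 2.-3 ends imaging at new therapy, so a progression documented after therapy in the same month should be rare.
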